2.2 Analysis sets

For each completed cohort, the data analysis will be performed upon final database lock for the cohort, and the results will be reported while the study may be ongoing for subsequent cohorts. For all analysis sets, participants will be analyzed according to the study treatment(s) received.

The full analysis set (FAS) will include all participants who received any study drug.

The safety analysis set is defined similarly as the FAS.

The PK analysis set will include all participants with at least one available valid (i.e., not flagged for exclusion) PK concentration measurement, who received any study drug and with no protocol deviations that impact PK data.

The PD analysis set will include all participants with available PD data and no protocol deviations with relevant impact on PD data. This set will be used for the primary endpoint analysis.

The IG analysis set will include all participants with at least one available valid (i.e., not flagged for exclusion) IG concentration measurement, who received any biotherapeutic study drug and with no protocol deviations that impact IG data.

Table 2-1 Protocol deviations and exclusions

Deviation code	Text description	Data exclusion
TRT08	Canakinumab/placebo wrong medication pack number administered at Day 85 visit to participant CCI	If a participant randomized on placebo took active drug, the adverse events recorded after the date/time of administration of the active drug will be excluded from the analysis, They will be summarized separately. Conversely, If a participant randomized on active took placebo, the data will be analyzed as planned. The participant took half of the planned dose.
EXCL02A	Ongoing medical history impacting cognition(Not AD) – Participant CCI	The participant will be excluded from the PD analysis set.
M-OTH38	Participant CCI has a CSF collection not per protocol at Day 85 (Backup sample used, using a different tube)	An additional analysis of biomarkers in CSF may be conducted excluding the impacted CSF sample from the analysis.

Deviation code	Text description	Data exclusion
M-OTH38	Participant CCI has a CSF collection not per protocol at Day 85 (Day85 CSF sample was done 2 weeks after the other Day 85 assessments)	-PK: the PK ratio CSF/serum will not be calculated (see Section 2.8, ratios will be calculated only if serum and CSF samples were taken within a window +/- 2 days)Biomarkers: no impact on the analysis of biomarkers in CSF.

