### **12.1 Analysis sets**

For each completed cohort, the data analysis will be performed upon final database lock for the cohort, and the results will be reported while the study may be ongoing for subsequent cohorts. For all analysis sets, participants will be analyzed according to the study treatment(s) received.

The full analysis set (FAS) will include all participants who received any study drug. This set will be used for the primary endpoint analysis.

The safety analysis set is defined similarly as the FAS.

The PK analysis set will include all participants with at least one available valid (i.e., not flagged for exclusion) PK concentration measurement, who received any study drug and with no protocol deviations that impact PK data.

The PD (total target) analysis set for biotherapeutic agents will include all participants with available (total target) PD data and no protocol deviations with relevant impact on (total target) PD data.

The IG analysis set for biotherapeutic agents will include all participants with at least one available valid (i.e., not flagged for exclusion) IG concentration measurement, who received any biotherapeutic study drug and with no protocol deviations that impact IG data.

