**Table 17-1 Key Information on canakinumab**

canakinumab	
Reference	IB
Drug type	Human monoclonal antibody
Half-life	26 days
Five half-lives	130 days
Generic name	Canakinumab
Formulation	Subcutaneous
Maximal planned clinical dose	300 mg q4 weeks
Target	Anti-human interleukin-1 $\beta$ (IL-1 $\beta$ ) antibody
Pharmacology	Blocks the interaction of IL-1 $\beta$ with the IL-1 receptor (IL-1R), leading to inhibition of its downstream targets, thereby preventing IL-1 $\beta$ -induced gene activation and the production of inflammatory mediators.

canakinumab	
Metabolism	Elimination pathways for the IgG-type mAbs such as canakinumab are distinct from metabolic pathways of small molecules. The IgG-based molecules are cleared from the body by a combination of processes such as proteolysis by the liver, elimination by the reticuloendothelial system (RES) and nonspecific endocytosis.
Potential to interact with other drugs based on in vitro studies	No study was conducted with canakinumab or its mouse surrogate, 1BSUR, to investigate drug-drug interaction in non-clinical species.
Reference safety information (RSI)*	System organ classes (SOCs) in the reference safety information tables as of the latest IB include infections and infestations across all indications below, in addition to the following:  CAPS: 

• Nervous system disorders

 Periodic fever syndromes 

• Investigations (platelet count decreased)

 SJIA: 

• Gastrointestinal disorders

• Immune system disorders

• Investigations (transaminases increased, platelet count decreased, neutrophil count decreased, white blood cell count decreased)

 Oncology: 

• Investigations (blood creatine phosphokinase increased)

• Blood and lymphatic system disorders

 Gouty arthritis and Cardiovascular risk reduction: 

• No additional SOCs

 Based on similarities of the patient population with Alzheimer's disease (including elderly, hypertensive, diabetes, cardiovascular disease, chronic obstructive pulmonary disease), the RSI Table 6-5 from the Cardiovascular risk reduction program (CANTOS) will be used as the RSI table for this study.

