2.5 Analysis supporting primary objective(s)

The primary endpoint, NTB total score, includes nine validated components: 1-2) Wechsler Memory Scale Visual-Paired Associates immediate and delayed scores; 3-4); Wechsler Memory Scale Verbal-Paired Associates immediate and delayed scores; 5-6) Rey Auditory Verbal Learning Test (RAVLT) immediate and delayed scores; 7) Wechsler Memory Scale Digit Span; 8) Controlled Word Association Test (COWAT); and 9) Category Fluency Test (CFT). In order to reduce burden on sites and participants, components 1-4 will not be administered in EXPLAIN-AD.

For each of the remaining five components, a raw score is first converted to a standardized z-score using baseline mean and SD (calculated from all participants in the PD analysis set with baseline scores), and a total z-score is derived by averaging all resulting z-scores. A change from baseline is calculated as post-baseline z-score minus pre-treatment z-score, whereby a positive change indicates an improvement from baseline.

The primary analysis will be performed on the PD analysis set.

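### The primary NTB comparison is defined by treatment received, not by randomised arm, and has no rule for a participant who received both treatments

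*SAP*

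**What the plan says.** The rule on treatment assignment is general. SAP 2.2 states: "For all analysis sets, participants will be analyzed according to the study treatment(s) received". Protocol 12.1 has the same sentence.

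The rule reaches the primary endpoint in both documents, although they name different sets. Protocol 12.1 says of the full analysis set: "This set will be used for the primary endpoint analysis". SAP 2.5 says: "The primary analysis will be performed on the PD analysis set".

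SAP Table 2-1 lists a deviation coded TRT08: "Canakinumab/placebo wrong medication pack number administered at Day 85 visit to participant" (the identifier is redacted). Its handling text has three parts:
- Placebo participant who took active drug: "If a participant randomized on placebo took active drug, the adverse events recorded after the date/time of administration of the active drug will be excluded". The row adds that these events get their own separate summary.
- Active participant who took placebo: "If a participant randomized on active took placebo, the data will be analyzed as planned".
- A closing remark that the participant's intake was half the scheduled dose.

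The participant in the EXCL02A row is removed from the PD set. The TRT08 participant is not. SAP 2.5.2 marks intercurrent events as not applicable, and the primary estimand in SAP 1.2.1 does not say how treatment assignment is to be handled.

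**The concern.** The primary objective is to compare an agent with placebo after 1:1 randomisation. The protection that randomisation gives belongs to the groups as randomised. If the arm label follows what was dispensed, an event after randomisation decides who is compared with whom. No analysis by randomised arm appears in the readable text of either document, so no second result would show whether the label mattered.

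The rule is also incomplete. It allows for more than one treatment received but does not say which arm then applies. With a dispensing error on record, the programmer of the primary model must choose an arm for at least one person. If that person was randomised to placebo, the SAP gives no instruction for the NTB data. If the person was randomised to active, the instruction is to proceed as planned, and the plan in the same section is the as-received rule. The two statements are not reconciled.

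The safety side has a related tension. Safety is analysed by treatment received, yet the TRT08 row takes events that follow an active dose out of the main analysis for a placebo participant. It does not say how the separate summary relates to the canakinumab column.

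**Working it through.** **1. The plan's own figure.** Inputs from SAP 3.1 and protocol 12.8.1: difference 0.19, SD 0.38, 36 evaluable per arm, one-sided alpha 0.10, 15% dropout.

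- Standard error = 0.38 × √(2/36) = 0.0896.
- Power = Φ(0.19/0.0896 − 1.2816) = Φ(0.840) = 79.95%. The noncentral t gives 79.6%. The stated value of about 80% reproduces.
- Dropout: 36/0.85 = 42.4, so 43 per arm and 86 in total, as stated.

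Changing the arm label from received to randomised leaves these planned figures as they are.

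**2. The trial as it stands.** SAP 1.1 reports 34 randomised. An equal split of 17 per arm with no dropout is assumed.

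- Standard error = 0.38 × √(2/17) = 0.130.
- Power for 0.19 is about 57% (normal) or 56% (t).

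**3. Expected effect of one participant in the wrong arm.** Take a placebo participant with no drug effect who is counted as active. The active arm then has 18 members, of whom 17 carry the effect.

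- Expected difference = 0.19 × 17/18 = 0.179, a dilution of 1/18, or about 6%.
- Power (t) falls from about 56% to 53%.
- An active participant with the full effect who is counted as placebo gives the same result: 0.19 × (1 − 1/18) = 0.179.

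**4. Sensitivity of the estimate to one label.** Suppose the participant's change differs by d from the others. Leaving an arm of 17 and joining what becomes an arm of 18 moves the contrast by d/17 + d/18. With d = 1 SD = 0.38:

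- 0.0224 + 0.0211 = 0.043 z, about one third of the standard error (0.043/0.130 = 0.33).
- The sign depends on the participant and the direction of the move, so this is not a bias in a known direction.

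**5. Which way the recorded error went.** Protocol 17.1.4 gives the active administration as one 150 mg injection plus one placebo injection for the first two doses, then two 150 mg injections. Day 85 falls in the second phase. One placebo pack in place of one active pack gives 150 of 300 mg, exactly half, and the remark about half the dose directly follows the active-took-placebo rule. This is the natural reading. A placebo participant given one active pack would also have received half an active dose, and the row does not exclude that outright.

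**The case against.** The strongest reply is that the recorded case is minor and already handled. On the natural reading, the participant was randomised to canakinumab and had one reduced administration at Day 85. The instruction to analyse as planned speaks of the data in general, so it most naturally keeps that person in the active arm for efficacy as well. The conditional wording may simply avoid revealing an allocation. For this one participant, much of that stands.

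It does not settle the general rule. The primary comparison is still labelled by treatment received, mixed exposure has no arm, and the placebo-took-active branch, which the sponsor wrote into the table, is silent on NTB.

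Three stronger readings are tempting, and the documents do not support them.
- A reader might infer that a participant crossed over and will be moved to the other arm. Neither document says so. One wrong pack is recorded, and no reassignment is stated.
- A reader might make carry-over the main issue, because Table 17-1 gives 130 days for "Five half-lives" and Day 171 is only 86 days after Day 85. About 10% of a Day 85 dose would remain at the 26-day half-life (2^(−86/26) = 0.10). No passage treats that dose as cleared, and analysis by randomised arm would leave the residue in place, so it does not argue for the fix.
- A reader might conclude that adverse events are lost. They are taken out of the main analysis but reported separately. Keeping events after an active dose out of the placebo column is defensible. What is missing is a reconciliation with the as-received principle.

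**Conclusion.** The point holds as a defect of definition. In both documents the primary NTB contrast is by treatment received, no arm is defined for mixed exposure, and there is no NTB rule for a placebo participant who took active drug.

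The size is modest: about 6% expected dilution of 0.19 for one mislabelled participant, or about 0.04 z either way for one who lies 1 SD from the others, against a standard error of about 0.13. The second figure shows how sensitive a small data set is to one label. It should not be read as the expected bias.

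These figures assume an equal split of 34, no dropout, SD 0.38 as in the sample size section, one participant affected, and a full change of arm label. The documents do not state such a change for the TRT08 participant. If that participant was on active drug and stays in the active arm, the practical effect on the primary result is small. The correction is still worth making, because it settles the label in advance whichever way the error went.

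**What to change.** In SAP 2.2, and in protocol 12.1 if it is amended again:
- Analyse the NTB primary endpoint and the clinical efficacy endpoints (NTB composites, DSST, eCognitive, ECog, NPI) by randomised arm, regardless of dispensing errors.
- Keep treatment received for the safety, PK, immunogenicity and total-target analyses. Total target depends on exposure, so as-received is reasonable there even though it is a PD measure.
- State that the TRT08 participant stays in the randomised arm for efficacy. This works in either direction and need not reveal the allocation.
- Reconcile the TRT08 adverse-event rule with the as-received safety principle: say where the events after an active dose are shown and which denominator applies.

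The cost is a few sentences and a change of treatment variable in the efficacy programs. No new data are needed, and planned N and power are unchanged. The downside is slight dilution if a participant truly received the other treatment. At worst, one placebo participant with the full drug effect among 17 gives 0.19 × 16/17 = 0.179, again about 6%. The gain is therefore a comparison defined by randomisation and fixed beforehand, not a larger expected difference.

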2.2.1 Subgroup of interest

Subgroups of participants MCI or Mild AD and participants CCI positive or negative may be used for supplementary analyses of efficacy, if the sample size in the subgroup is sufficient.

2.3 Patient disposition, demographics and other baseline characteristics

2.3.1 Patient disposition

Participant disposition will be presented using the Safety set for all participants and by actual treatment received. The following summaries will be provided:

- Number (%) of participants who completed treatment and those who discontinued the study treatment phase along with the primary reason for study discontinuation
- At IA only: Number (%) of participants who are still on-treatment (based on the 'EOC1 (or EOC2 if applicable) disposition page not completed)

Participant disposition data will be listed.

2.3.2 Demographics and other baseline characteristics

Demographic and other baseline data including disease characteristics will be listed and summarized descriptively by treatment group for all participants in the FAS.

Categorical data will be presented as frequencies and percentages. For continuous data, mean, standard deviation, median, minimum, and maximum will be presented.

Relevant medical histories and current medical conditions at baseline will be listed by treatment, participant, system organ class and preferred term.

2.4 Treatments (study treatment, rescue medication, concomitant therapies, compliance)

2.4.1 Study treatment / compliance

The duration of exposure in months to each treatment arm as well as dose intensity (computed as the ratio of actual cumulative dose received and actual duration of exposure) and the relative dose intensity (computed as the ratio of dose intensity and planned dose intensity) will be summarized by means of descriptive statistics using the safety set.

2.4.2 Prior, concomitant and post therapies

Concomitant medications and significant non-drug therapies prior to and after the start of the study treatment will be listed according to the Anatomical Therapeutic Chemical classification system, by treatment group and for all participants.

2.5 Analysis supporting primary objective(s)

The primary endpoint, NTB total score, includes nine validated components: 1-2) Wechsler Memory Scale Visual-Paired Associates immediate and delayed scores; 3-4); Wechsler Memory Scale Verbal-Paired Associates immediate and delayed scores; 5-6) Rey Auditory Verbal Learning Test (RAVLT) immediate and delayed scores; 7) Wechsler Memory Scale Digit Span; 8) Controlled Word Association Test (COWAT); and 9) Category Fluency Test (CFT). In order to reduce burden on sites and participants, components 1-4 will not be administered in EXPLAIN-AD.

For each of the remaining five components, a raw score is first converted to a standardized z-score using baseline mean and SD (calculated from all participants in the PD analysis set with baseline scores), and a total z-score is derived by averaging all resulting z-scores. A change from baseline is calculated as post-baseline z-score minus pre-treatment z-score, whereby a positive change indicates an improvement from baseline.

The primary analysis will be performed on the PD analysis set.

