## 5.2 Exclusion criteria

### IMPORTANT

The exclusion criteria for the core protocol are located in this section ([Section 5.2](#)). These exclusion criteria apply to all participants enrolled into this study. However, there may also be additional cohort specific exclusion criteria which are provided in [Section 17](#) for each of the investigational agents.

Participants fulfilling any of the following criteria and any criteria detailed in the cohort-specific information ([Section 17](#)) are not eligible for inclusion in this study. No additional exclusions may be applied by the investigator, in order to ensure that the study population will be representative of all eligible participants.

1. Exclusion criterion #1 has been revised and is now replaced as #1a.
- 1(a) Exclusion criterion #1(a) has been revised and is now replaced as #1(b).
- 1(b) Use of an investigational agent or an approved product with the intent to modulate inflammation or modulate the course of AD (e.g., Tau ASOs, gene therapy, amyloid or tau vaccine):
  - Previous use of small molecules is allowed if discontinued for at least five half-lives, or at least 30 days from when the expected pharmacodynamic effect has returned to baseline prior to screening, whichever is longer
  - Previous use of monoclonal or polyclonal antibodies or other biologics is allowed if discontinued for at least five half-lives prior to screening
2. Exclusion criterion #2 has been revised and is now replaced as exclusion #2a.
- 2(a) Current medical or neurological condition that in the judgement of the investigator, might impact cognition or performance on cognitive assessments, e.g., MCI not due to AD, non-Alzheimer dementia, Huntington's disease, Parkinson's disease, stroke, schizophrenia, bipolar disorder, active major depression, multiple sclerosis (MS), amyotrophic lateral sclerosis (ALS), active seizure disorder, or history of traumatic brain injury associated with loss of consciousness and ongoing residual transient or permanent neurological signs/symptoms including cognitive deficits, and/or associated with skull fracture.
3. Exclusion criterion #3 has been deleted and this exclusion # will not be replaced.
4. Exclusion criterion #4 has been revised and is now replaced as exclusion #4(a).
- 4(a) Diagnosis of vascular dementia prior to baseline (e.g., modified Hachinski Ischaemic Scale score > 6 or those who meet the NINDS-AIREN criteria for vascular dementia).

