### **Sponsor staff**

The following unblinded sponsor roles are required for this study:

- Unblinded clinical staff managing drug re-supply to site
- Unblinded sample bioanalyst(s) (e.g., PK, PD)

Sponsor clinical staff are required to assist in the management and re-supply of investigational drug product. These individuals are not provided with randomization lists directly, but may be unblinded through communication of drug re-supply needs.

The sample analysts will receive a copy of the randomization schedule (via request to the Randomization Office), to facilitate analysis of the samples. The sample analysts will provide the sample data to the study team under blinded conditions unless otherwise allowed.

The trial statistician will be able to access the randomization list for interim analyses and is allowed to share unblinded information with the rest of the clinical team as appropriate for internal decision purposes, as outlined in [Table 6-1](#). For example, unblinded summaries and unblinded individual data can be shared with the team for interim analyses.

Study programmers and other personnel involved in study data analysis are allowed to access treatment assignment information for the purpose of conducting interim analyses. CCI

The clinical trial team is allowed to share unblinded results with other sponsor staff (e.g. decision boards) as required for internal decision making on the study or the project at the time of interim analyses while the study is ongoing.

All unblinded personnel will otherwise keep randomization lists and data or information that could unblind other study team members confidential and secure except as described above.

Following final database lock for each investigational agent, all sponsor roles may be considered unblinded.

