**Table 6-1** **Blinding levels**

Role	Time or Event			Commercially Confidential Information
	Randomization list generated	Treatment allocation & dosing	Safety event (single participant unblinded)	
Participants	B	B	B	
Site staff	B	B	B	
Unblinded site staff (see text for details)	NA	NA	NA	
Drug Supply and Randomization Office	UI	UI	UI	
Unblinded sponsor staff (see text for details)	UI	UI	UI	
Statistician/statistical programmer/data analysts	UI	UI	UI	
Independent committees used for assessing interim results	B	UI	UI	
All other sponsor staff not identified above	B	B	UI	

B Remains blinded

NA Not applicable

UI Allowed to be unblinded on individual patient level

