### **8.3 Efficacy/Pharmacodynamics**

Efficacy/pharmacodynamics of each drug regimen will be based on the following general classes of assessments:

- Cognitive assessment

- Assessments of neuropsychiatric symptoms and function (activities of daily living)
- Imaging of microglia activation in a subset of participants
- Total target for biotherapeutic agents

Pharmacodynamic (PD) samples will be collected, as defined in the Assessment Schedule (Table 8-1), with specific time points of each collection detailed in the Cohort-specific Section 17. Follow instructions outlined in the Site Operations Manual regarding sample collection, numbering, processing, and shipment.

In order to better define the PD profile, the timing of the sample collection may be altered based on emergent data. The number of samples/blood draws and total blood volume collected and total CSF volume collected will not exceed those stated in the protocol. PD samples will be obtained and evaluated in all participants and for all agents.

PD samples will be obtained and evaluated in all participants at all dose levels, including the placebo group.

Completed clinical efficacy assessments will be reviewed and examined by the investigator for responses that may indicate potential adverse events (AEs) or serious adverse events (SAEs). The investigator should review not only the responses to the clinical assessments but also any unsolicited comments from the participant. If AEs or SAEs are confirmed, then the physician must record the events as per instructions given in the protocol.

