### **11.2 Database management and quality control**

Novartis personnel (or designated CRO) will review the data entered by investigational staff for completeness and accuracy. Electronic data queries stating the nature of the problem and requesting clarification will be created for discrepancies and missing values and sent to the investigational site via the EDC system. Designated investigator site staff are required to respond promptly to queries and to make any necessary changes to the data.

Concomitant treatments and prior medications entered into the database will be coded using the World Health Organization (WHO) Drug Reference List, which employs the Anatomical Therapeutic Chemical classification system. Medical history/current medical conditions and adverse events will be coded using the Medical Dictionary for Regulatory Activities (MedDRA) terminology.

Randomization codes and data about all study treatment (s) dispensed to the participant and all dosage changes will be tracked using an Interactive Response Technology (IRT). The system will be supplied by a vendor, who will also manage the database. The data will be sent electronically to Novartis (or a designated CRO) at specific timelines.

Each occurrence of a code break via IRT will be reported to the clinical team and monitor. The code break functionality will remain available until study shut down or upon request of Novartis.

Once all the necessary actions have been completed and the database has been declared to be complete and accurate, it will be locked **and the treatment codes will be unblinded** and made available for data analysis. Any changes to the database after that time can only be made after written agreement by Novartis development management.

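### The SAP moves the primary NTB analysis from the protocol's FAS to a deviation-filtered PD set, keeps no FAS run, and does not list the change

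*SAP*

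**What the plan says.** **Population.** Protocol 12.1: "The full analysis set (FAS) will include all participants who received any study drug. This set will be used for the primary endpoint analysis". Protocol 12.4.2 names the FAS again for the MMRM. SAP 2.2 keeps the same FAS definition but assigns the primary endpoint to the PD analysis set, and SAP 2.5 confirms it: "The primary analysis will be performed on the PD analysis set". Membership of that set requires available PD data and no deviation judged to have a relevant impact on them. SAP Table 2-1 removes one participant under EXCL02A, for an ongoing condition other than AD that affects cognition.

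**z-score reference.** Protocol 12.4.1 takes the baseline mean and SD from everyone randomised who has baseline scores. SAP 2.5 takes them from PD-set members with baseline scores.

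**Model.** Protocol 12.4.2 also adjusts for baseline prognostic factors, with age and MMSE as examples. The SAP 2.5.1 model has NTB baseline and its interaction with visit, but no such factors. SAP 2.5.4 allows, without committing to, sensitivity models with factors such as age and educational level; MMSE is not named.

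**Fallback and disclosure.** Neither SAP 2.5.4 nor 2.5.5 names the FAS; the SAP uses it for demographics and baseline data (2.3.2). The visible text of SAP 4, the section for changes to protocol-specified analyses, reports only that the planned PET interim will not take place. SAP 2.1, meanwhile, says that the analysis follows protocol section 12 and uses data from all who consented.

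**The concern.** The main issue is the population. Who counts in the primary contrast depends on a judgement about impact, applied to a term that the documents use in two ways. Protocol 12.1 confines the set to total target: "The PD (total target) analysis set for biotherapeutic agents will include all participants with available (total target) PD data". Protocol 8.3 puts cognition and pharmacodynamics under one heading: "Efficacy/pharmacodynamics of each drug regimen will be based on the following general classes of assessments". The SAP drops the total-target qualifier and does not say what PD data are. Table 2-1 then removes someone for a cognition-related deviation, which fits the broad reading. Two programmers could build different primary sets.

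The visible text has no rule that membership is fixed blind to treatment. With 34 randomised, each exclusion weighs more than it would have at 86, and no planned NTB result would show a reader whether an exclusion mattered. Someone who consulted SAP 4 would not learn that population, scale and model all differ from the protocol.

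The z-score reference and the covariates are secondary. They are departures from the protocol that should be recorded, not sources of bias.

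**Working it through.** **1. The plan's own figure.** Inputs from protocol 12.8.1 and SAP 3.1: difference 0.19, SD 0.38, 36 evaluable per arm, one-sided alpha 0.10. Normal approximation: 0.5/sqrt(2/36) = 2.121; 2.121 − 1.282 = 0.840; power 79.9%. The noncentral t gives 79.6%. The other rows of the table come out at 66.1%, 49.7% and 41.3%, against 66%, 50% and 41% stated. 36/0.85 = 42.4, so 43 per arm and 86 in total. The planning figures reproduce and are not at issue.

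**2. Evaluable numbers.** SAP 1.1 gives 34 randomised at termination; the arm split and the number with week-24 data are not given. I assume 17 per arm as the upper end (1:1, complete data) and 12 per arm as the lower end.

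**3. Leverage of one exclusion.** If a participant lies c SDs from the mean of an arm of n, leaving that participant out moves the arm mean by c × 0.38/(n − 1).

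| n | c | Shift (z) | Share of 0.19 |
|---|---|---|---|
| 17 | 0.67 | 0.67 × 0.38/16 = 0.016 | 8% |
| 17 | 2 | 2 × 0.38/16 = 0.048 | 25% |
| 12 | 0.67 | 0.67 × 0.38/11 = 0.023 | 12% |
| 12 | 2 | 2 × 0.38/11 = 0.069 | 36% |

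The direction is unknown. If exclusion is unrelated to outcome within arm, the expected shift is zero. On the broad reading of PD data, participants with no post-baseline NTB contribute nothing to the contrast under either set, so the exposure is confined to those removed for deviations.

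**4. Power at 0.19 (two-sample noncentral t, one-sided 0.10).** 17:17 gives 56.3% and 17:16 gives 55.4%. 12:12 gives 46.8% and 12:11 gives 45.7%. Losing one participant costs about one point.

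**5. Re-basing.** Assume all 34 have baseline scores and one is removed, c SDs from the baseline mean. The SD of the remaining 33 relative to the original is sqrt((33 − (34/33)c²)/32), and a component's z-scale changes by the inverse.

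- c = 0: SD ratio 1.0155, scale −1.5%
- c = 2: SD ratio 0.950, scale +5.3%
- c = 2.5: SD ratio 0.911, scale +9.8%
- c = 3: SD ratio 0.861, scale +16.1%

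The reference mean cancels out of a change score, and the factor is the same in both arms.

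**6. Covariates.** This is a single-visit ANCOVA approximation, not the MMRM. Adding k covariates multiplies the variance of the contrast by (1 − R²)(1 + k/(N − k − 3)), where R² is the share of residual variance they explain. With N = 34 and k = 2 the second factor is 1 + 2/29 = 1.069, so break-even is R² = 1 − 1/1.069 = 6.5%. Counting NTB baseline as already in the model (k from 1 to 3) gives 6.7%. At assumed R² of 0, 5%, 10% and 20% the SE changes by +3.4%, +0.8%, −1.9% and −7.5%. The documents give no R², so the sign of the effect is unknown.

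**The case against.** The strongest defence is that the one named exclusion is an eligibility matter. EXCL02A corresponds to core exclusion 2(a): "Current medical or neurological condition that in the judgement of the investigator, might impact cognition or performance on cognitive assessments". A condition present before dosing cannot be caused by treatment, and leaving that person out introduces no expected bias unless the choice was driven by outcome. Table 2-1 also names the deviations and their handling, although it is not said to be exhaustive. This stands, and it is why no bias is claimed. It supports a supportive analysis without that participant; it does not explain having no FAS run at all.

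A reader might go further and infer that unblinded staff chose the exclusions, or that the type I error is inflated. The documents do not support that. Table 6-1 lists "Statistician/statistical programmer/data analysts" as allowed individual-level unblinding from list generation, but that is a permission. The text of protocol 6.4 ties access to a purpose: "The trial statistician will be able to access the randomization list for interim analyses". The planned PET interim was cancelled, although SAP 1.1 still permits others. Protocol 11.2 says that after lock "the treatment codes will be unblinded". SAP 2.13 has the trial statistician run the DMC analyses without saying whether blinded, but describes that committee as looking at cohort progress and safety. Parts of the blinding and interim text are redacted, so a rule may exist out of view. What remains is that the visible text does not close the gap.

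Two further points are fair. A leaner model is defensible at 34 participants, and the protocol's covariates were examples rather than a fixed list. Also, both documents analyse by treatment received, so restoring the FAS would not produce an as-randomised analysis.

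**Conclusion.** The point holds as an undisclosed and avoidable change to the primary analysis population, worth correcting. The texts conflict plainly on set and z-score reference, the primary model drops the prognostic adjustment, and nothing planned shows the NTB result on the FAS.

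Its size is a matter of leverage, not of demonstrated bias. With 12 to 17 evaluable per arm, SD 0.38 and one participant 0.67 to 2 SD from the arm mean, the shift is 0.016 to 0.07 z, or 8% to 36% of 0.19, in an unknown direction. The excluded participant's arm and outcome are not given. Power is about 47% to 56% whichever set is used.

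The other two changes concern consistency with the protocol. Re-basing acts equally in both arms: −1.5% to about +5% on a component if the removed baseline score is within 2 SD of the mean, up to about +16% at 3 SD. Dropping the adjustment affects precision, and could help or hurt depending on whether R² is below or above about 6.5%.

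**What to change.** **SAP 2.2 and 2.5.** Run the primary NTB MMRM on the FAS, with z-scores standardised on all randomised participants with baseline scores, as in protocol 12.4.1. Keep the PD-set analysis as supportive, define PD data for it, and fix its exclusions before unblinding. At minimum, add a definite FAS sensitivity run.

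**SAP 2.5.1 and 2.5.4.** Either restore the age and MMSE adjustment, or keep the leaner model with a stated reason (34 randomised) and make the age- and MMSE-adjusted model a definite sensitivity analysis.

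**SAP 4.** List and justify every departure that remains.

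**Cost.** SAP wording and one extra model run. One participant with an eligibility deviation stays in the primary set. If age and MMSE return to the primary model, two degrees of freedom are used and, on the approximation above, the SE could rise by about 3.4% if they explain nothing; the either/or lets the sponsor avoid this.
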